6.4 STUDY INTERVENTION COMPLIANCE

Full compliance with the intervention is defined as completing the entire first session, the MRI session, and providing at-home saliva samples. As the intervention is applied and monitored by research personnel, compliance can be directly observed.

6.5 CONCOMITANT THERAPY

Eligible participants will be permitted to be receiving concomitant therapy, such as therapy, antidepressants, or other medications. Given that the current trial investigates target engagement acutely from stimulation, there is no investigation in changes of symptoms. Thus, exploratory analyses will consider individual differences that can be explained by differences in concomitant interventions. The only medications not permitted during this trial are anticonvulsants and recent benzodiazepines. The use of antidepressants or other therapies is unlikely to affect our outcome, as our primary and secondary outcomes are with respect to a single session.

Concomitant therapies will be logged at the first session. Participants will be requested to include the dosing for these therapies (i.e., how often per day, how much in each pill, how many pills) as well as when they were first prescribed the medication.

6.5.1 RESCUE MEDICINE

N/A

7. STUDY INTERVENTION DISCONTINUATION AND PARTICIPANT DISCONTINUATION/WITHDRAWAL

7.1 DISCONTINUATION OF STUDY INTERVENTION

Discontinuation of stimulation during session 1 means that study participation is halted and no other sessions are completed. If a clinically significant finding is identified after enrollment, the investigator or qualified designee will determine if any change in participant management is needed. Any new clinically relevant finding will be reported as an adverse event (AE).

The study intervention (i.e., 40 minutes of stimulation spaced by intermittent resting-states) will be discontinued for the following reasons:

- Any clinical adverse event (AE), laboratory abnormality, intercurrent illness or other medical condition, or situation occurs such that continued participation in the study would not be in the best interest of the participant.
- The participant meets any exclusion criteria (either newly developed or not previously recognized).

7.2 PARTICIPANT DISCONTINUATION/WITHDRAWAL FROM THE STUDY

Participants are free to withdraw from participation in the study at any time upon request.

An investigator may discontinue or withdraw a participant from the study for the following reasons:

- Any clinical adverse event (AE), laboratory abnormality, intercurrent illness or other medical condition, or situation occurs such that continued participation in the study would not be in the best interest of the participant.
- The participant meets any exclusion criteria (either newly developed or not previously recognized).

The reason for participant discontinuation or withdrawal from the study will be recorded with the participant files. Participants who sign the informed consent form and are not randomized will be replaced. Participants who sign the informed consent form, are randomized, and receive the full or part of the study intervention (40-minutes of stimulation on session 2), and subsequently withdraw from the study, are withdrawn from the study, or discontinue the study will not be replaced. However, participants who sign the informed consent form, and are not randomized will be replaced.

7.3 LOST TO FOLLOW-UP

A participant will be considered lost to follow-up if he or she fails to return for 1 scheduled visit and is unable to be contacted by the study site staff. All efforts will be made to ensure participants are not lost to follow-up, including developing rapport and ensuring enrolled participants are reminded of their session dates. To ensure that participants attend the follow-up MRI session, research personnel will be flexible in timing, including offering this session later in the day as well as some weekends. Furthermore, the at-home saliva sample can be returned at any time.

Every effort will be made to contact participants who are lost to follow-up, including contacting via email and phone. However, if a participant is lost to follow-up, the missed session will be labeled as missing data and our pre-determined analysis plan takes into consideration missing data. Of note, neither the primary nor secondary outcomes are dependent on the MRI session or at-home saliva samples.

8. STUDY ASSESSMENTS AND PROCEDURES

8.1 EFFICACY ASSESSMENTS

Inclusion and exclusion criteria will be determined at the initial session, including concomitant therapies, medical history, and diagnosis, to ensure that participants are diagnosed with MDD, with low suicide risk, and free of benzodiazepines and anticonvulsant medications.

8.1.1 ELECTROPHYSIOLOGY

1. Resting-state EEG (RSEEG) recordings will be completed several times during the second session. Eyes-open and eyes-closed RSEEG will be collected before any task are performed or stimulation is delivered. Then, after every task block without and with stimulation, two-minutes of eyes-open RSEEG are collected. This measure is used to determine the immediate after-effects of tACS on brain activity, specifically on phase-amplitude coupling between delta oscillations in prefrontal electrodes and beta oscillations in left motor electrodes and between theta oscillations in prefrontal electrodes and gamma oscillations in bilateral parietal-occipital electrodes.
2. Phase-amplitude coupling between delta-beta and theta-gamma oscillations will be acquired during task performance of the EEfRT as measured in our previous study (Riddle, Alexander et al., in review) and similar to our previous study with delta-beta tACS and theta-gamma tACS (Riddle, McFerren et al. 2021).

8.1.2 TASK PERFORMANCE

1. Goal-directed behavior: In the Expenditure of Effort for Reward Task (EEfRT), goal-directed behavior is quantified as the percentage of trials in which the participant chose the HARD task instead of the EASY task. In our previous experiment, goal-directed behavior negatively and significantly correlated with anhedonia symptom severity. Goal-directed behavior ranges from 0 to 100% and task difficulty is titrated to push goal-directed behavior down to <85%. In our previous use of this task, minimum goal-directed behavior was 23%. Thus, we expect performance to range from approximately 23-85%.
2. Reward-evaluation: In the EEfRT, reward-evaluation is quantified as the slope of the linear fit of percentage HARD trials for each incentive level (\$2.50 to \$6 in \$0.50 increments), dependent variable, to the incentive level, independent variable. In our previous experiment, reward-evaluation positively and significantly correlated with trait anxiety severity in participants with depression. In our previous experiment, the average reward evaluation was 15% per \$1.

8.1.3 CLINICAL EVALUATIONS

1. MINI INTERNATIONAL PSYCHIATRIC INTERVIEW FOR THE DSM-V (MINI) is a structured interview that is an abbreviation of the Structured Clinical Interview for the DSM (Sheehan, Lecrubier et al. 1998). The MINI is ideal for the diagnosis of MDD and to be used as screening technique for exclusion diagnoses. These data are used to determine eligibility after the first session.
2. HAMILTON DEPRESSION RATING SCALE (HAM-D) is a 17-item assessment that determines depression severity (Hamilton 1960). This assessment is used to complement the BDI-II. Items within the HAM-D have been shown to capture different dimensions of MDD, such as anhedonic and anxious-somatic symptoms. This scale is also used to determine suicide risk. Items are summed to a total score ranging 0 to 54.
3. COLUMBIA-SUICIDE SEVERITY RATING SCALE (C-SSRS) is used to screen for suicide risk (Posner, Brown et al. 2011). In the event that a participant reports plans or intention to commit suicide, then an acute psychiatric assessment is conducted by [name].
4. MAUDSLEY STAGING METHOD (MSM) is a method for measuring treatment resistance in participants with depression on a scale of 3 to 15 (mild = 3-6; moderate = 7-10; severe=11-15)(Donaldson, Poon et al. 2009).

8.1.4 SELF-REPORT ASSESSMENTS

1. The Beck Depression Inventory (BDI) (Spielberger et al. 1983) will be administered at session 1. The BDI is a 21-item, self-report rating inventory that measures characteristic attitudes and symptoms of depression. Scores range from 0 to 63.
2. The Behavioral Inhibition and Behavioral Activation Self Report Scales (BIS/BAS) (Carver and White 1994) will be completed during the first session. These scales are used to monitor the perceived sensitivity to reward and punishment. BIS/BAS is broken into four sub-scores: BIS (7 to 28), BAS drive (4-16), BAS fun-seeking (4-16), and BAS reward (7-20).
3. The State-Trait Anxiety Inventory (STAI) (Spielberger et al. 1983) will be completed during the first session. These 40 items are used to quantify frequencies of feelings of anxiety. STAI has two subscores, state and trait anxiety, range 20 to 80.
4. The Snaith-Hamilton Pleasure Scale (SHAPS) (Snaith, Hamilton et al. 1995) will be completed online before the first session to stratify randomization and again at the first session. This scale is used to assess anhedonia, range 14 to 56.
5. Patient Health Questionnaire-9 (PHQ-9) is a 9-item assessment that mirrors the criteria for major depressive disorder (Kroenke, Spitzer et al. 2001). This assessment is used as a screening tool that is completed prior to the first in-person session to increase the feasibility of the study by only running sessions with participants that will most likely be diagnosed with MDD, an inclusion criterion. Range 0 to 27.
6. Temporal Experience of Pleasure Scale (TEPS) is an 18-item assessment that quantifies symptoms of anhedonia along two sub-dimensions: consummatory (8 to 48) and anticipatory (10 to 60) (Gard, Gard et al. 2006). This assessment may provide additional insight into subtypes of anhedonia symptoms and is acquired during the first session.
7. Ruminative Responses Scale (RRS) is a 22-item assessment that quantifies the degree to which participants engage in depressive rumination, range 31 to 155 (Nolen-Hoeksema, Larson et al. 1999). This assessment is completed at the first session.

8.2 SAFETY AND OTHER ASSESSMENTS

1. The Columbia Suicide Severity Rating Scale (C-SSRS) (Posner, Brown et al. 2011) will be administered by trained research personnel at the first session to thoroughly assess suicide risk. If a participant reports experiencing either suicidal ideation or suicidal behavior, research personnel will collect more information from the participant to deliver to either [name] or [name]. Clinical personnel will decide if an acute assessment is required. Acute assessment may include facilitating contact of the participant with their psychiatrist or primary care physician to establish a plan for safety, continued care, and follow-up. If the participant does not have an established provider, [name] or [name] will assist in establishing a care plan. If at any point during the assessment, the participant is deemed an imminent risk of harm to self or others, study personnel will enlist the aid of campus security to ensure that the participant is safely escorted to the Emergency Department for further care. [name] and/or [name] will decide if participation should be stopped after the acute assessment. If an acute assessment is required, then participation will be halted.
2. A structured interview probing for the experience of adverse events based on the responses from the stimulation side effects questionnaire will be completed after stimulation on the second session. [name], [name], or [name] will use the completed interview to assess the severity of the adverse event and its relationship to the study intervention.
3. A stimulation side effects questionnaire will be administered at the end of each stimulation session. This tool will be used as a safety measure and to collect data on the participant's experience. A similar questionnaire was used in a previous study (IRB# 13-2995) to determine ability to successfully blind the participants using sham transcranial current stimulation.

8.3 ADVERSE EVENTS AND SERIOUS ADVERSE EVENTS

8.3.1 DEFINITION OF ADVERSE EVENTS (AE)

Adverse event means any untoward medical occurrence associated with the use of an intervention in humans, whether considered intervention-related (21 CFR 312.32 (a)).

8.3.2 DEFINITION OF SERIOUS ADVERSE EVENTS (SAE)

An adverse event (AE) or suspected adverse reaction is considered "serious" if, in the view of the investigator, it results in any of the following outcomes: death, a life-threatening adverse event, inpatient hospitalization or prolongation of existing hospitalization, a persistent or significant incapacity or substantial disruption of the ability to conduct normal life functions, or a congenital anomaly/birth defect. Important medical events that may not result in death, be life-threatening, or require hospitalization may be considered serious when, based upon appropriate medical judgment, they may jeopardize the participant and may require medical or surgical intervention to prevent one of the outcomes listed in this definition. Examples of such medical events include allergic bronchospasm requiring intensive treatment in an emergency room or at home, blood dyscrasias or convulsions that do not result in inpatient hospitalization, or the development of drug dependency or drug abuse.

8.3.3.2 RELATIONSHIP TO STUDY INTERVENTION

All adverse events (AEs) must have their relationship to study intervention assessed by the principal investigator and co-investigator(s) who examines and evaluates the participant based on temporal relationship and their clinical judgment. The degree of certainty about causality will be graded using the categories below. In a clinical trial, the study product must always be suspect.

- **Definitely Related** – There is clear evidence to suggest a causal relationship, and other possible contributing factors can be ruled out. The clinical event, including an abnormal laboratory test result, occurs in a plausible time relationship to study intervention administration and cannot be explained by concurrent disease or other drugs or chemicals. The response to withdrawal of the study intervention (dechallenge) should be clinically plausible. The event must be pharmacologically or phenomenologically definitive, with use of a satisfactory rechallenge procedure if necessary.
- **Probably Related** – There is evidence to suggest a causal relationship, and the influence of other factors is unlikely. The clinical event, including an abnormal laboratory test result, occurs within a reasonable time after administration of the study intervention, is unlikely to be attributed to concurrent disease or other drugs or chemicals, and follows a clinically reasonable response on withdrawal (dechallenge). Rechallenge information is not required to fulfill this definition.
- **Potentially Related** – There is some evidence to suggest a causal relationship (e.g., the event occurred within a reasonable time after administration of the trial medication). However, other factors may have contributed to the event (e.g., concomitant events). Although an AE may initially be flagged as requiring more information and later be upgraded to "definitely related", as appropriate.
- **Unlikely to be related** – A clinical event, including an abnormal laboratory test result, whose temporal relationship to study intervention administration makes a causal relationship improbable (e.g., the event did not occur within a reasonable time after administration of the study intervention) and in which other drugs or chemicals or underlying disease provides plausible explanations (e.g., concurrent treatments)'s clinical judgment.
- **Not Related** – The AE is completely independent of study intervention administration, and/or evidence exists that the event is definitely related to another etiology. There must be an alternative, definitive etiology documented by the clinician.

8.3.3.3 EXPECTEDNESS

The principal investigator ([name]), with input from the co-investigators ([name] and [name]) when necessary, will determine whether an adverse event (AE) is expected or unexpected in this population. The principal investigator ([name]) is an expert in non-invasive brain stimulation and will provide his expert opinion in regard to this as well. An AE will be considered unexpected if the nature, severity, or frequency of the event is not consistent with the risk information previously described for the study intervention.

8.3.4 TIME PERIOD AND FREQUENCY FOR EVENT ASSESSMENT AND FOLLOW-UP

The occurrence of an adverse event (AE) or serious adverse event (SAE) may come to the attention of study personnel during study visits, or the study participant may report AE or SAEs outside of a scheduled study visit.

All AEs including local and systemic reactions not meeting the criteria for SAEs will be captured on the appropriate case report form (CRF). Information to be collected includes event description, time of onset, clinician's assessment of severity (assessed only by those with the training and authority to make a diagnosis), and time of resolution/stabilization of the event. All AEs occurring while on study must be documented appropriately regardless of relationship. All AEs will be followed to adequate resolution. Any medical condition that is present at the time that the participant is screened will be considered as baseline and not reported as an AE. However, if the study participant's condition deteriorates at any time during the study, it will be recorded as an AE. Changes in the severity of an AE will be documented to allow an assessment of the duration of the event at each level of severity to be performed. AEs characterized as intermittent require documentation of onset and duration of each episode.

Research personnel will record all reportable events with start dates occurring any time after informed consent is obtained until 7 (for non-serious AEs) or 30 days (for SAEs) after the last day of study participation. At each study visit, research personnel will inquire about the occurrence of AE/SAEs since the last visit. Events will be followed for outcome information until resolution or stabilization. All AEs including local and systemic reactions not meeting the criteria for SAEs will be captured on the appropriate case report form (CRF). Information to be collected includes assessment of severity, relationship to study product (assessed only by those with the training and authority to make a diagnosis), and time of resolution/stabilization of the event. All AEs occurring while on study must be documented appropriately regardless of relationship. All AEs will be followed to adequate resolution.

Any medical condition that is present at the time that the participant is screened will be considered as baseline and not reported as an AE. However, if the condition deteriorates during the study, it will be recorded as an AE.

Changes in the severity of an AE will be documented to allow an assessment of the duration of the event at each level of severity to be performed. AEs characterized as intermittent require documentation of onset and duration of each episode.

Research personnel will record all reportable events with start dates occurring any time after informed consent is obtained until 7 (for non-serious AEs) or 30 days (for SAEs) after the last day of study participation. At each study visit, the investigator will inquire about the occurrence of AE/SAEs since the last visit. Events will be followed for outcome information until resolution or stabilization.

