1.3 SCHEDULE OF ACTIVITIES (SOA)

| | Phone Screening | Online Assessments | Session 1 Clinical Assessments | Session 2 - Stimulation | Session 3 - MRI |
|--------------------------------|-----------------|--------------------|--------------------------------|-------------------------|-----------------|
| Procedures | | | | | |
| Informed consent | X (verbal) | X (digital) | X (written) | | |
| Determine Eligibility | X | X | X | | |
| PHQ-8 (without suicide q.) | | X | | | |
| PHQ-9 | | | X | | |
| SHAPS | | X | X | X | |
| Demographics | | | X | | |
| Medical history | | | X | | |
| MINI (diagnostic) | | | X | | |
| C-SSRS | | | X | | |
| Maudsley Staging Method | | | X | | |
| HAM-D | | | X | | |
| RRS | | | X | | |
| BIS/BAS | | | X | | |
| SHAPS | | | X | | |
| C-SSRS | | | X | | |
| TEPS | | | X | | |
| Beck Depression Inventory - II | | | X | | |
| BAS/BIS | | | X | | |
| STAI | | | X | | |
| Urine Pregnancy Test | | | | X | |
| Randomization | | | | X | |
| Resting-state EEG | | | | X | |
| EEfRT | | | | X | |
| EEfRT with tACS | | | | X | |
| Intermittent resting-state EEG | | | | X | |
| Stimulation Questionnaire | | | | X | |
| AE Structured Interview | | | | X | |
| AE Review and Evaluation | | | | * | |
| Structural MRI | | | | | X |
| Resting-state MRI | | | | | X |
| Functional MRI with EEfRT | | | | | X |

* when applicable

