For the third session, participants are instructed to arrive at the Biomedical Research Imaging Center (BRIC) in Marsico Hall on UNC-CH campus. Participants are instructed to arrive at the facility 30 minutes early to ensure that they are ready to go into the MRI for the 60-minute allotted timeslot. During the 60 minutes of scanning, a 5-minute structural MR is acquired, 10-minutes of functional MR scans during the eyes-open resting-state are acquired, and the remaining time is used to complete as many blocks of the EEfRT as possible. Completion of the MRI session is not required for the dataset to be considered a complete dataset. These additional data acquisitions enable exploratory analyses that will be used to design future studies.

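### Adverse-event inquiry is promised at every visit and recording runs to 7 or 30 days after participation, but the schedule marks AE activity only at the stimulation session and has no scheduled contact after the MRI session

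*Combined protocol and SAP*

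**What the plan says.** Section 8.3.4 makes two commitments. The first is on frequency: "At each study visit, research personnel will inquire about the occurrence of AE/SAEs since the last visit". The section repeats the rule a few paragraphs later with a different person asking: "At each study visit, the investigator will inquire about the occurrence of AE/SAEs since the last visit". The second is on duration: reportable events are recorded from informed consent "until 7 (for non-serious AEs) or 30 days (for SAEs) after the last day of study participation". The same section also recognises that participants may report events between visits.

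The schedule in Section 1.3 has five contact columns: "Phone Screening | Online Assessments | Session 1 Clinical Assessments | Session 2 - Stimulation | Session 3 - MRI". Two rows concern AEs. The interview row reads "AE Structured Interview | | | | X", which puts its only mark in the fourth column, Session 2. The row "AE Review and Evaluation" is also marked only at Session 2, with a footnote that it applies when needed. Section 8.2 agrees on the timing of the interview, which "will be completed after stimulation on the second session".

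On the MRI visit, Section 4.1 says: "Completion of the MRI session is not required for the dataset to be considered a complete dataset". Section 5.5 describes it as a session to which participants are invited back. Section 7.1 says that if stimulation is discontinued, participation stops and no further sessions take place. An AE is among the listed reasons for discontinuing.

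**The concern.** An AE window means something only if the plan says how events inside it come to light. Here the text sets a rule for every visit and two windows after participation, while the table that staff work from shows AE activity on one day only. Staff who follow the table would not ask at the MRI visit.

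The larger issue is who has no later visit at all. Someone whose stimulation is stopped because of an AE does not proceed to Session 3, so the inquiry that Section 8.3.4 requires at each visit never arises for that person after the stimulation day. The same holds for anyone who does not attend the MRI. Absence of a later inquiry can therefore depend on how the participant tolerated stimulation, which is an undesirable kind of gap in safety data. What is at stake is the completeness of late AE and SAE records, not the efficacy analysis.

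**Working it through.** No figure in the plan needs reproducing. The check sets the sections side by side and counts.

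**AE activity by contact**

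| Contact | AE items marked in 1.3 | Inquiry required by 8.3.4 |
|---|---|---|
| Session 1, clinical assessments | 0 | Yes, as a study visit |
| Session 2, stimulation | 2, one of them when applicable | Yes |
| Session 3, MRI | 0 | Yes, as a study visit |
| Any contact after Session 3 | none scheduled | not applicable |

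**Does the Session 2 interview substitute for the general inquiry?** No. Sections 4.1 and 9.4.5 tie it to side effects that the participant rated at the top of the questionnaire scale on the day of stimulation. It cannot pick up anything that begins afterwards.

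**Where the windows fall.** Both are counted from the last day of participation. The last scheduled contact is, at the latest, on that day. So the number of scheduled contacts inside either window is 0, including for someone who completes all three sessions. The synopsis gives participation as 2 weeks, so for a participant who uses all of it the windows close at about:

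- non-serious AEs: 14 + 7 = day 21;
- SAEs: 14 + 30 = day 44.

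Section 4.4 ends the study at the 48th participant's final session, which for the last participants is before these dates.

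**Three paths through the plan**

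1. *Attends the MRI.* Section 8.3.4 requires an inquiry at Session 3 covering the time since stimulation, and Section 1.3 omits it. After Session 3 only self-report remains.
2. *Completes stimulation, does not attend the MRI.* The last scheduled AE assessment is on the stimulation day.
3. *Stimulation discontinued.* Section 7.1 ends participation, so the last scheduled AE assessment is again on the stimulation day. That section speaks of session 1, whereas the schedule places stimulation in Session 2. I read it as meaning the stimulation session.

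**Other routes in the text.** Section 8.3.4 follows AEs to resolution, but this applies to events already known. Section 7.3 provides e-mail and telephone attempts for participants lost to follow-up, but does not say that they will be asked about AEs.

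**The case against.** The strongest reply is that the windows are recording rules, not a promise of active follow-up. Section 8.3.4 says which events are recorded by start date, and names self-report outside visits as a route. For MRI attendees the inquiry is already required in the text, so for them the defect is a missing mark in a table. Stimulation is confined to one session, Section 2.3.1 describes its side effects as mild and transient, and Section 6.1.1 reports a non-significant-risk designation. Much of this stands. It limits the point to a modest reconciliation plus a gap for participants with no later visit. It does not close that gap, because neither self-report nor the contact attempts in Section 7.3 include an AE question.

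Several stronger readings are tempting, and the documents do not support them:

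- *Reported rates would be stimulation-day rates labelled as 7- or 30-day rates.* Section 9.4.5 analyses only the stimulation questionnaire and the structured interview. No rate over either window is planned, so none can be mislabelled.
- *The MRI visit is optional.* Section 6.4 counts it in full compliance, and Section 7.3 treats it as a scheduled visit and describes flexible timing to secure attendance. The exact statement is that it is not required for a complete dataset.
- *Participants without an MRI are never contacted again.* Section 7.3 provides contact attempts. What is missing is scheduled contact with an AE question.
- *A two-week follow-up visit has been left out of the schedule.* Section 10.1.7.1 mentions such a visit, but Section 7.3 calls the MRI a follow-up session and participation lasts 2 weeks. It is plausibly Session 3 under another name.
- *A specific number of the 48 would be missed.* Any such number would rest on an assumed non-attendance rate.

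**Conclusion.** The point holds as a conflict between text and schedule, with a selective gap in late AE ascertainment. Section 8.3.4 requires an inquiry at each visit, and the schedule shows AE activity at Session 2 only. Participants who do not attend the MRI or whose stimulation is discontinued have no scheduled inquiry after the stimulation day. For all participants, 0 scheduled contacts fall inside the 7- or 30-day window, so events there depend on unprompted report.

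The number of participants on the second and third paths cannot be derived from the documents. The conclusion rests on reading the schedule as the complete list of planned contacts. It does not depend on any claim about how often late events occur after this stimulation, or on whether participants who feel worse return less often. It is a cheap improvement to safety data and does not threaten the primary or secondary outcome.

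**What to change.** 1. In Section 1.3, mark the AE/SAE inquiry in the Session 3 column so that the table matches Section 8.3.4. At the same time, settle whether research personnel or the investigator asks, since the section says both.
2. Send every participant who received any stimulation, including those who discontinue or do not attend the MRI, a short AE/SAE check by REDCap or e-mail at the end of the 7-day and 30-day windows, and have staff review the replies. REDCap already collects the self-report assessments, and e-mail is already used for reminders.
3. If the sponsor does not want these checks, state in Section 8.3.4 that events after the last visit are captured by spontaneous report only.

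Steps 1 and 2 cost a mark in the schedule, two short messages and a few minutes of staff time per participant. Step 3 costs one sentence, but leaves late events to be volunteered.
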